3.2 Study Outcome Measures

3.2.1 Primary Outcome Measures

Safety

The following parameters will be evaluated for each dose and formulation of *Na*-APR-1 (M74) alone or co-administered with *Na*-GST-1:

1. Frequency of solicited injection site and systemic reactogenicity, graded by severity, on the day of each study vaccination through 14 days after each study vaccination.
2. Frequency of study vaccine-related serious adverse events from the time of the first study vaccination through approximately 9 months after the last study vaccination.
3. Frequency of clinical safety laboratory adverse events.
4. Frequency of unsolicited adverse events, graded by severity, from the time of each study vaccination through approximately 1 month after each study vaccination.
5. Frequency of new-onset chronic medical conditions through approximately 9 months after the third study vaccination.
6. Frequency of Adverse Events of Special Interest through approximately 9 months after the third study vaccination.

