4 STUDY DESIGN

The study will be conducted as a randomized, placebo-controlled, double-blind Phase 1 dose-escalating clinical trial in healthy adult volunteers living in the hookworm-endemic area of Americaninhas, Brazil.

Prior to beginning study-related activities, the consent and cooperation of local municipal government leaders and representative community members will be sought, after which volunteers will be invited to participate in the study. After providing written informed consent and passing the informed consent comprehension questionnaire, volunteers will undergo eligibility screening, including a complete medical history, physical examination, hematology testing, serum glucose testing, liver and renal function testing, HIV antibody testing, Hepatitis B and C serology, and urinalysis; urine pregnancy testing will be performed on all female volunteers. In addition, all volunteers will be tested for serum IgE antibodies to *Na*-APR-1 (M74) and *Na*-GST-1, and a fecal examination will be performed for ova and parasites. All clinically significant abnormalities will be reviewed with volunteers and referral for follow-up care will be provided. After screening, those volunteers determined to be eligible, based on the inclusion and exclusion criteria, will be invited to participate in the study.

Sixty volunteers will be progressively enrolled into 1 of 6 Groups over a projected 3-month enrollment period, with each subject followed for 13 months post-enrollment (to Study Day 380). Group enrollment will be done in an open sequential fashion, whereas within each Group, investigational product (IP) assignment and vaccination will be done in a randomized double-blind fashion.

The first 20 subjects will be entered into Groups 1 and 2

- Group 1 double-blind IP assignment (n=10):
 - 5 subjects will receive 10µg *Na*-APR-1 (M74) delivered by IM injection in the deltoid muscle, with sterile saline administered to the alternate arm.
 - 5 subjects will receive 10µg *Na*-APR-1 (M74) delivered by IM injection in the deltoid muscle, with 100µg *Na*-GST-1 administered to the alternate arm.
- Group 2 double-blind IP assignment (n=10):
 - 5 subjects will receive 10µg *Na*-APR-1 (M74) plus 5µg GLA-AF delivered by IM injection in the deltoid muscle, with sterile saline administered to the alternate arm.

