11 STATISTICAL CONSIDERATIONS

11.1 Study Hypotheses

This study is not designed to statistically test a specific hypothesis. Rather, it is intended to assess the safety, reactogenicity, and immunogenicity of two novel vaccines being co-administered to humans for the first time. The chosen sample size principally facilitates the assessment of safety, as discussed in Section 11.2, *Sample Size Considerations*. Given that, this study will explore, primarily by using descriptive statistics, to assess the following hypotheses:

1. Co-administration of the Na-APR-1 (M74)/Alhydrogel[®] and Na-GST-1/Alhydrogel[®] vaccines will not increase the reactogenicity or safety risk above that of either administered alone.
2. Co-administration of the Na-APR-1 (M74)/Alhydrogel[®] and Na-GST-1/Alhydrogel[®] vaccines will not decrease the functional activity of induced IgG antibodies to either antigen compared to when either is administered alone.
3. Co-administration of the Na-APR-1 (M74)/Alhydrogel[®] and Na-GST-1/Alhydrogel[®] vaccines will not decrease the IgG antibody response to either antigen compared to when either is administered alone.
4. Co-administration of the Na-APR-1 (M74)/Alhydrogel[®] and Na-GST-1/Alhydrogel[®] vaccines will not decrease the avidity of induced IgG antibodies to either antigen compared to when either is administered alone.
5. Co-administration of the Na-APR-1 (M74)/Alhydrogel[®] and Na-GST-1/Alhydrogel[®] vaccines will not decrease the induction of specific MBCs to either antigen compared to when either is administered alone.

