11.3 Planned Interim Analyses

11.3.1 Safety Review

Descriptive and hypothesis-testing approaches will be used to estimate AE rates and to compare these rates in the difference doses and formulations of *Na*-APR-1 (M74) alone or co-administered with *Na*-GST-1. Estimates will be presented with their 95% confidence intervals. Formal statistical tests, as outlined below, will be used to compare doses. No formal adjustments for multiple comparisons will be made. Statistical tests will use a two-sided significance level of 5%.

The proportion of subjects with at least one injection site AE will be compared by vaccine allocation (e.g., *Na*-APR-1 (M74) vs. *Na*-APR-1 (M74) co-administered with *Na*-GST-1), by *Na*-APR-1 (M74) dose, and by GLA-AF dose.

Laboratory results (hematological and clinical chemistry) will be examined for trends over time and any clinically significant values for individuals will be reported.

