- Line listings of clinical and laboratory AEs classified as immediate (within the first 60 minutes), systemic, and local will be displayed in tables stratified by dose cohort and formulation of Na-APR-1 (M74) and formulation (i.e., no GLA-AF or 5 µg GLA-AF).
- AEs will be summarized by severity and relationship to vaccine formulation by individuals and dose of Na-GST-1, Na-APR-1 (M74), and GLA-AF.
- The frequency of vaccine-related SAEs will be tallied as well as summarized by body system, by vaccine formulation and dose cohort.

Primary Outcome Measures:

The following summary parameters will be evaluated for each dose and formulation of Na-APR-1 (M74) alone or co-administered with Na-GST-1:

1. Frequency of solicited injection site and systemic reactogenicity, graded by severity, on the day of each study vaccination through 14 days after each study vaccination.
2. Frequency of study vaccine-related serious adverse events from the time of the first study vaccination through approximately 9 months after the last study vaccination.
3. Frequency of clinical safety laboratory adverse events.
4. Frequency of unsolicited adverse events, graded by severity, from the time of each study vaccination through approximately 1 month after each study vaccination.
5. Frequency of new-onset chronic medical conditions through approximately 9 months after the third study vaccination.
6. Frequency of Adverse Events of Special Interest through approximately 9 months after the third study vaccination.

Analysis Plan:

The proportion of participants with at least one injection site AE will be compared by Na-APR-1 (M74) vaccine formulation and dose cohort and co-administration status with Na-GST-1. We will test the null hypotheses that the type and number of adverse events is the same across all groups by Fisher's exact test.

Laboratory results (hematological and clinical chemistry) will be examined for trends over time and any clinically significant values for individuals will be reported.

Secondary Objective: To assess the impact of co-administering Na-APR-1 (M74) and Na-GST-1 on antibody production by measuring the antibody levels to each antigen on study Day 126.

Secondary Outcome Measures:

The following parameters will be evaluated for each dose and formulation of Na-APR-1 (M74) alone or co-administered with Na-GST-1:

1. The IgG level by an indirect enzyme-linked immunosorbent assay (ELISA) on approximately Day 126.

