15.4 Timing/Reports

In addition to the study-related documentation required by the regulatory authorities, 4 study reports will be generated. These include 2 interim SMC safety reports, 1 interim safety and immunogenicity study report, and the final study report. The first interim SMC safety report will be completed after the safety data from the Day 14 visits of Group 2 have been compiled, for the purposes of deciding whether it is safe to precede with enrollment into Group 3 of the study. The second interim SMC safety report will be completed after the safety data from the Day 14 visits of Group 4 have been compiled, for the purposes of deciding whether it is safe to precede with enrollment into Group 5 of the study. The interim study report will be compiled after interim safety and primary immunogenicity data (i.e., antigen-specific IgG responses to *Na*-GST-1 and *Na*-APR-1 (M74) as determined by ELISA) from all Day 140 visits is available and the study investigators unblinded. This report will serve as the basis for deciding whether to continue with

future Phase 1 testing of the vaccines in children. A final report containing all safety and immunology data will be prepared after trial completion.

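### The all-groups Fisher test of AE ‘type and number’ does not suit recurrent AE counts and does not isolate Na-GST-1 versus saline, the only randomised factor

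*Protocol*

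**What the plan says.** Section 11.4 of the protocol (Primary Objective, Analysis Plan) has two sentences on AE comparisons.

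- The first is at participant level: "The proportion of participants with at least one injection site AE will be compared by" formulation and dose cohort of Na-APR-1 and by co-administration status.
- The second names the test: "We will test the null hypotheses that the type and number of adverse events is the same across all groups by" Fisher's exact test. Section 11.4 sets the level at 5%, two-sided.

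Section 11.3.1, the interim safety review, says AE rates will be estimated and that tests will be used "to compare these rates in the difference doses and formulations of" Na-APR-1, alone or co-administered. The only endpoint it specifies for this is again local: "The proportion of subjects with at least one injection site AE will be compared by vaccine allocation", by dose and by GLA-AF.

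The primary outcomes are wider. Section 3.2.1 opens with "Frequency of solicited injection site and systemic reactogenicity, graded by severity" and goes on to unsolicited AEs, among others.

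On design, Section 4 fills Groups 1–6 (dose and GLA-AF) by open sequential enrolment, and "within each Group, investigational product (IP) assignment and vaccination will be done in a randomized double-blind fashion". Each Group of 10 has 5 on saline and 5 on Na-GST-1. The first hypothesis in Section 11.1 is that co-administration "will not increase the reactogenicity or safety risk above that of either administered alone".

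**The concern.** **Unit of analysis.** Fisher's test assumes that each unit is classified once and independently. A number of adverse events is a count that one person can add to after each of three vaccinations, and people who react once tend to react again. If events are pooled by group and tested, the effective sample is smaller than the test assumes and false signals become more likely.

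**Contrast.** Only Na-GST-1 versus saline is randomised. Dose and GLA-AF follow enrolment order. A null of equality across all groups asks whether anything differs anywhere. It does not ask whether co-administration raises risk, which is the part of the first safety hypothesis that randomisation within this trial can answer.

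**Stakes.** Section 15.4 says of the interim study report: "This report will serve as the basis for deciding whether to continue with" Phase 1 testing in children. That report and the final analysis should speak to co-administration safety. For systemic and unsolicited AEs, a non-significant all-groups result says little about it, and a significant one does not identify it.

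**Working it through.** **The plan's own figures.** The only safety probabilities given are in Section 11.2, from 1 − (1 − p)^n. For example, 1 − 0.90^20 = 87.84%, 1 − 0.95^30 = 78.54% and 1 − 0.97^60 = 83.92%. All 15 table entries reproduce. They concern seeing at least one event and say nothing about the Fisher test.

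**Inputs from the protocol.** 60 participants; six Groups of 10 split 5:5 (Section 4), so 30 versus 30; three vaccinations (Section 2.2.2), with AEs collected after each (Section 3.2.1); two-sided 5% (Section 11.4).

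**Assumptions.** The protocol gives no planning AE rates by arm and no within-subject correlation. All rates and ICCs below are assumed.

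**Step 1: unit of analysis.** With m records per subject, pooling inflates the variance by about 1 + (m − 1) × ICC. For m = 3 and ICC 0.4 this is 1 + 2 × 0.4 = 1.8. The nominal cut-off of 1.96 then acts like 1.96/√1.8 = 1.46, a two-sided error near 14%. For m = 6 and ICC 0.4 it is 3.0, the cut-off is 1.13 and the error is near 26%. Fisher's test is conservative, so simulation comes out lower. Type I error of Fisher's test on pooled events (beta-binomial, 30 versus 30, no true difference, 20,000 trials per setting):

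| Base rate | Records per subject | ICC 0.1 | ICC 0.2 | ICC 0.4 |
|---|---|---|---|---|
| 10% | 3 | 4.5% | 6.6% | 10.6% |
| 10% | 6 | 8.0% | 12.9% | 21.9% |
| 20% | 3 | 5.3% | 7.3% | 11.3% |
| 20% | 6 | 9.0% | 14.2% | 23.0% |
| 40% | 3 | 5.6% | 7.6% | 12.2% |
| 40% | 6 | 8.8% | 14.1% | 23.5% |

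At ICC 0 with three records the error is about 3.5%, so the excess comes from correlation. With the participant as unit (any AE, yes or no), full enumeration of the 30 versus 30 Fisher test gives a maximum size of 2.74%, at p = 0.5. A within-Group permutation test on per-subject counts (C(10,5) = 252 splits per Group, base rate 40%) has size 3.2–4.3%.

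**Step 2: contrast.** Let Na-GST-1 raise the rate from 20% to 50% in every Group. Each Group's expected rate is (5 × 0.20 + 5 × 0.50)/10 = 35%, so the six-Group null is true and the effect cannot be seen. Over 12 cells of 5 it is visible but spread over 11 degrees of freedom. Rejection rates (8,000 trials; the all-groups test is Freeman–Halton; the stratified test is the exact conditional test with Groups as strata):

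| Saline vs Na-GST-1 | Six Groups | 12 cells | 30 vs 30 Fisher | Stratified exact |
|---|---|---|---|---|
| 20% vs 50% | 2.8% | 25.3% | 58.7% | 59.1% |
| 10% vs 30% | 3.0% | 14.8% | 38.0% | 38.7% |
| 10% vs 40% | 2.4% | 31.1% | 70.3% | 70.5% |
| 30% vs 60% | 2.9% | 23.5% | 56.9% | 57.3% |

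Enumeration of the 30 versus 30 Fisher test at 20% versus 50% gives 59.6%, in line with the simulated 58.7%.

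**Step 3: what a rejection means.** With no Na-GST-1 effect but rates that differ by dose or Group:

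| Assumed rates | Six Groups | 12 cells | 30 vs 30 Fisher | Stratified exact |
|---|---|---|---|---|
| 30/40/50% by dose | 12.6% | 7.8% | 2.3% | 2.6% |
| 20/40/60% by dose | 47.0% | 29.6% | 1.8% | 2.6% |
| 15/25/35/55/60/80% by Group | 79.2% | 59.6% | 1.3% | 2.4% |
| 10/40/80% by dose | 98.0% | 91.1% | 0.6% | 2.4% |

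The first two columns are power against the all-groups null, not error. They show that a rejection need not involve co-administration.

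**Step 4: does stratifying matter?** At equal Group rates it costs nothing (Step 2). With unequal rates and an odds ratio of 4, four settings give stratified versus unstratified power of 63.2 vs 62.1%, 58.2 vs 53.7%, 55.0 vs 45.4% and 44.0 vs 27.8%.

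**The case against.** The strongest reply is that the sentence is brief, not wrong. Section 11.4 says it only outlines methods and leaves detail to an analytical plan, which is not available here. The preceding sentence is at participant level and lists co-administration status, so Fisher's test can be read as the test for those comparisons. Nothing in the protocol describes pooling events. The highest error rates need six records per subject and an ICC of 0.4; with three records the range is 4.5–12.2%. AEs are also to be tabulated by co-administration status, and estimates are promised with 95% confidence intervals. The trial is declared unpowered and mainly descriptive. An unstratified 30 versus 30 test is not misled by dose. The quoted sentence is not in Section 11.3.1, on which the interim report draws.

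Much of this stands. On the participant-level reading, the unit problem is one of wording. The injection-site comparison is valid, and failing to stratify it loses some power but not validity. The all-groups rejections are not errors.

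What remains is the contrast. The protocol fixes a null and a test, and the all-groups test is the only one Section 11.4 fixes for systemic and unsolicited AEs. Section 11.3.1 says AE rates in general will be compared, but ties no endpoint or test to this beyond injection-site AEs. Having committed to tests at 5%, an unpowered trial has the more reason to aim them at the randomised question. For antibody levels, Section 11.4 does make Na-GST-1 an explicit factor.

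**Conclusion.** The point holds. As written, the all-groups Fisher test does not suit AE counts, and under either meaning of groups it does not isolate Na-GST-1 versus saline. For an assumed 20% versus 50%, it rejects in 2.8% of trials over the six Groups or 25% over the 12 cells, against about 59% for a direct participant-level comparison. If events are pooled, type I error runs from near nominal (4.5%) to 23.5%. These figures rest on assumed rates and ICCs. The loss of the contrast over the six Groups follows from the 5:5 split itself when the Na-GST-1 effect is the same in every Group.

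The consequence is moderate. Dose escalation rests on Safety Monitoring Committee review and the halting rules of Section 9.5, and injection-site AEs already have a sound comparison. The gap is in systemic and unsolicited AEs. The text should be changed, but the trial's conduct is not in question.

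**What to change.** In Section 11.4, and in Section 11.3.1, which feeds the interim report:

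- Make the participant the unit: any AE of each class, and worst grade.
- Compare Na-GST-1 with saline by an exact test stratified by the six Groups, with a risk difference and 95% confidence interval, for injection-site, systemic and unsolicited AEs.
- If AE numbers are compared, use a per-subject count method such as a within-Group permutation test.
- Keep any all-groups test as descriptive, define which groups it covers, and do not read it as evidence on co-administration.

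The cost is rewording one sentence in each section and slightly more analysis work. Sample size, visits and data collection do not change.
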